Study Protocol and Statistical Analysis Plan

Hearing aid performance study for different
spatial configurations

Version: 1

02.08.2022

NCT05284903

Hearing aid performance study for different spatial configurations

1 Background

Hearing aids are designed to amplify and transmit sound to compensate for impaired hearing.

The main objective of this medical device is to improve the perception of speech, which can be defined among many attributes by intelligibility or listening effort. Evaluating the performance of the hearing aid or different features reasonably assumes that the talker location should be in front and close of the hearing aid user. However, listening situations in daily life might show much more variability regarding the spatial configuration of the talker, listener and noise sources.

This investigation is designed to extend the evaluation of hearing aid features to different spatial configuration and also to evaluate the benefit of the investigational device. The investigational device is CE marked and will be used within its defined use and on the intended population. The investigation is divided into three independent parts:

- Beamformer benefit: the first part of the study will evaluate the effect of a wider beamformer on intelligibility and listening effort for a speech-in-noise condition when the talker is not in front of the listener in comparison to a narrower beamformer (StereoZoom),
- Speech Enhancer benefit: the second part of the study will evaluate the effect of the Speech Enhancer algorithm on distant speech in quiet and when speech in quiet is coming from an adjacent room with different measures such as listening effort, objective and subjective speech intelligibility,
- Hearing aid benefit: the third part of the study will evaluate the benefit provided by amplification with a speech-in-noise test where the talker is in front and close to the hearing aid user.

This investigation should provide further knowledge about the perception of speech in different listening conditions with different spatial configurations. Results from the investigation should provide additional input to the development of further products.

2 Objectives

The primary objective for the beamformer benefit part is

(1) to evaluate whether I-BF provides better SRTs in noisy situation with speech from side and behind than with the R-BF with hearing impaired listeners (moderate to severe hearing loss) during a lab test session. Expected SRT improvement based on previous data is about 1 dB SNR with the I-BF and SRTs are measured with the OLSA test. Tested null hypothesis: there is no difference between the RBF and the I-BF.

Secondary objective for the beamformer benefit part is

(2) to evaluate whether I-BF provides less listening effort in noisy situation with speech from side and behind than with the R-BF with hearing impaired listeners (moderate to severe hearing loss) during a lab test session. Tested null hypothesis: there is no difference between the R-BF and the I-BF measured with the ACALES test with varying SNR.

Secondary objectives for the Speech Enhancer benefit part are:

(3) to evaluate whether the investigational device with Speech Enhancer activated provides less listening effort than without speech enhancer for distant speech in a quiet listening situation for people with moderate to severe hearing loss. Tested null hypothesis: there is no difference between Speech Enhancer activated or not measured with the ACALES test with varying distance.

(4-a) to evaluate whether the investigational device with Speech enhancer activated provides better speech intelligibility than without speech enhancer for distant speech in a quiet situation for people

with moderate to severe hearing loss. Tested null hypothesis: there is no difference between Speech Enhancer activated or not measured with the WaKo Rhyme Test.

(4-b) to evaluate whether the investigational device with Speech enhancer activated provides better speech intelligibility than without speech enhancer for speech from an adjacent room in a quiet situation for people with moderate to severe hearing loss. Tested null hypothesis: there is no difference between Speech Enhancer activated or not measured with the WaKo Rhyme Test.

(5-a) to evaluate whether the investigational device with Speech enhancer activated provides better subjective speech intelligibility and less listening effort than without speech enhancer for distant speech in a quiet situation without access to visual cues for people with moderate to severe hearing loss. Tested null hypothesis: there is no difference between Speech Enhancer activated or not with the subjective assessment questionnaire.

(5-b) to evaluate whether the investigational device with Speech enhancer activated provides better subjective speech intelligibility and less listening effort than without speech enhancer for distant speech in a quiet situation with access to visual cues for people with moderate to severe hearing loss. Tested null hypothesis: there is no difference between Speech Enhancer activated or not with the subjective assessment questionnaire.

(5-c) to evaluate whether the investigational device with Speech enhancer activated provides better subjective speech intelligibility and less listening effort than without speech enhancer for speech from an adjacent room a quiet situation without access to visual cues for people with moderate to severe hearing loss. Tested null hypothesis: there is no difference between Speech Enhancer activated or not with the subjective assessment questionnaire. Secondary objectives for the Hearing aid benefit part are:

3 Identification and description of the investigational device

In this clinical investigation, the investigational device will be used according to its intended use. The intended use of the hearing aid is to amplify and transmit sound to the ear and thereby compensate for impaired hearing.

4 Design of the clinical investigation

This clinical investigation is an interventional study, executed at one investigation site, with a confirmatory design. The investigation model is single group, with a randomized test order where the test conditions are fully crossed-over. It is a single blinded study because all test conditions are implemented in the same hearing aid, so that the tested condition cannot be identified by the test participant.

The tested conditions for the primary and secondary objectives are programmed in the investigational device, the CE marked Phonak Audeo P-90-R. The tested features can be activated via the MyPhonak APP by the subjects/investigator.

5 Risks and benefits of the investigational device and clinical Investigation

The product-related risks and the clinical investigation procedure-related risks are well controlled during the clinical investigation as the participant will always be under the supervision of the investigator. Even if the residual risk probabilities range from remote (1:100'000 – 1:1'000'000) to incredible (< 1:10.000.000), any adverse effect will be recorded, reported and monitored during the clinical investigation.

The clinical investigation shall provide data to confirm the superiority of the I-BF over the RBF in listening situations where the dominant talker is not located in the front of the hearing aid user. These data shall be used as input for further product improvement and more efficient use of existing feature.

The clinical investigation shall provide data to confirm the superiority of the Speech Enhancer in communication situations with a distant talker. These data shall be used as evidence for further marketing communications and more efficient use of existing feature.

Better perception in different situations has been identified as one of the key elements to provide satisfaction to the hearing aid users (Picou, 2020). Therefore, the overall risk/benefit ratio is considered to be acceptable for this clinical investigation.

6 Endpoints

1) Oldenburg Sentence Test: Speech reception threshold (SRT)

The measure of the speech reception threshold (SRT) is a procedure to evaluate the speech intelligibility in different listening conditions. The SRT in noise is defined as the signal-to-noise ratio (SNR) needed to understand 50% of the presented sentences. The SRT can be obtained with an adaptive procedure to overcome floor and ceiling effects, where the SNR is adapted based on the intelligibility score of the previous sentence. The adaptive procedure is defined so that the test conditions lead to a SNR with 50 % speech intelligibility: the SNR for the next sentence is decreased (more difficult situation) when the presented sentence is correctly understood or the SNR is increased (easier situation) when the presented sentence is not correctly understood. For the adaptive procedure, the noise is presented at fixed 65 dB level and the speech level is adapted according the reference procedure. The Oldenburg Sentence Test (OLSA) is a standard speech intelligibility test in German (Wagener et al., 1999 a-b-c) recommended for the evaluation of hearing aid performances (Kollmeier et al., 2011). The OLSA test uses nonsense sentences with equivalent difficulty. The OLSA test was already used for previous evaluations of the R-BF with the talker located in the front (Neher et al., 2017). The OLSA will be repeated in 8 times for the primary objective: 2 test conditions (R-BF and I-BF) by two talker locations (speech from the side and speech from the back) by two test sessions (test at visit 1 and retest at visit 2); in 3 test conditions for the secondary objective with the speaker from the front: unaided, aided with Fixed Directional and aided with Stereo Zoom. The SRT (in dB SNR) is provided for each OLSA measure.

2) ACALES: Listening effort

To determine listening effort in different situations, speech stimuli are presented in different conditions. The listening effort is subjectively rated on a predefined on a 13-point categorical scale (Luts et al, 2010) with varying difficulties (SNRs or talker distance). As speech stimuli the OLSA sentences are either presented at different levels in a background noise with fixed level or at different distances from the listener in a quiet environment. This creates different SNRs (speech levels at the position of the listener), which can be predefined or automatically adapted by the ACALES procedure (Krueger et al., 2017). ACALES adaptively chooses the SNRs or talker distances for each presentation on the basis of previous ratings. The procedure is rapid and easy to administer, resolves differences between individuals and masker conditions, and offers a high test-retest reliability (Krueger et al., 2017). Following data are provided by the ACALES procedure:

For the beamformer benefit part: for each subject the result is a two-slope curve that provides the SNR for following effort scale categorical units (ESCU) "no effort" (1), moderate effort (7), and "extreme effort" (13). The ACALES test will be repeated in 8 times: 2 test conditions (RBF and I-BF) by

two talker locations (speech from the side and speech from the back) by two test sessions (test at visit 1 and retest at visit 2).

For the Speech Enhancer part: for each subject the results are the different effort scale categorical units (ESCU) from 1= “no effort” to 13 = “extreme effort” determined at 2m, 4m and 8m. The ACALES test will be repeated in 6 times: 2 test conditions (Speech Enhancer ON and OFF) by three talker distances (2m, 4m, 8m) in just one test session.

3) WaKo Rhyme Test : speech intelligibility

The measure of the speech perception in % is an alternative procedure to evaluate the speech intelligibility in different listening conditions. The Speech perception is defined as % correct words out of a word list of 72 words. Initially an individual presentation level is measured using adaptive procedure to determine the level necessary to understand 50% of all presented words. Afterwards the correct word score can be obtained using this individual presentation level (reduced by 1 dB) by calculating the ratio of correct words by the number of total words.

The Rhyme Test (WAKO) is a standard speech intelligibility test in German (v. Wallenberg & Kollmeier, 1989) recommended for the evaluation of hearing aid performances. The WAKO test uses words with equivalent difficulty in an open design. The WAKO test was already used for previous evaluations of the SE (Appleton-Huber, 2020). The WAKO will be repeated 4 times for the secondary objective: 2 test conditions (SE ON and SE OFF) by two listening situations (speech from adjacent room with door left ajar, speech in reverb). Following data are provided from each WAKO measure: test list number and speech score (in %).

4) Subjective assessment

In addition to the tests mentioned above a subjective assessment will be used to determine the subjective perception as this measure is often a good indication for clinical relevance. For this purpose a novel is either read by the tester aloud (with soft voice) or presented by a loudspeaker in a reverberant room in three different distances (2, 4m, 8m) and in an adjacent room with door left ajar. The subjects rates his/her perception of the presented real and recorded speech using a questionnaire on the dimensions “loudness, listen effort and speech intelligibility”. The subject will rate the perception on the same scale with pencils with different colors to get either absolute and relative ratings. The subjective assessment will be repeated 14 times for the secondary objective: 2 test conditions (SE ON and SE OFF), read out loud by the tester (with visual cues) and presented via loudspeaker (no visual cues) by three different distances (2m, 4m, 8m) and in an adjacent room with the door left ajar presented via loudspeaker. Following data are provided from assessment: rating on a 100-point scale per condition and per dimension.

7 Inclusion and Exclusion Criteria

Subjects fulfilling all of the following inclusion criteria are eligible for the investigation:

- Experienced (minimum use duration 6 months) and adult (minimum age: 18 years) hearing aid users,
- Written and spoken German,
- Ability to understand instruction,
- Ability to describe listening experiences,
- Ability to attend to the appointments,
- Healthy outer ear,
- Hearing loss within the fitting ranges of the investigational product,

- Informed consent as documented by signature.

The presence of any one of the following exclusion criteria will lead to the exclusion of the subject:

- Clinical contraindications deformity of the ear (closed ear canal or absence of pinna)
- Known hypersensitivity or allergy,
- Not willing to wear the hearing aid,
- Fluctuating hearing that could influence the results.

8 Measurements and procedures

1) Otoscopy

The investigator will assess the ear and the ear canal status with an otoscope before the first hearing test. The investigator will start the assessment at the outer ear, continue with the ear canal and the ear drum in the end. Doing this, he/she will check if there are any contra indications for fitting hearing aids or further tests. The investigator has to report the amount of wax in the ear canal and also any potential irritation, inflammation, or the presence of foreign objects. A clear and clean ear canal is mandatory to fit the hearing aids and to take part to the clinical investigation.

2) Audiometry

Before the audiometry the ear canal will be inspected with a standard ear microscope. The pure-tone audiometry is common audiological measurement tool to assess a persons, frequency specific, hearing. The hearing threshold levels (HTL) are measured via air (AC) and bone conduction (BC) for each side independently as well as uncomfortable levels (UCL).

The measurement is done via headphones for the air conduction or a special transducer for the bone conduction. The measurement for the hearing threshold typically starts on the participants, subjective, better ear at 1000 Hz. The investigator presents a pure-tone and slowly increases to level, in 5 dB steps, until the participant indicate that he/she can just hear the tone. The measures are repeated 2 times to verify the reported threshold. The same procedure is repeated for each test frequency.

3) OLSA and ACALES tests (beamformer benefit)

For the beamformer benefit part: diffuse cafeteria babble noise from 11 loudspeakers at 65.0 dB (marked with "N"). Target speech material from 90° (marked with "T") or 180° are OLSA sentences. Subjects are seated in the middle of the loudspeaker circle and are instructed to look to the front.

Material of the ACALES procedure presented via 3 loudspeakers in a distance of 2m, 4m, and 8m measured from the subject's position in a reverberant environment.

4) WaKo speech intelligibility test (SE benefit)

Speech material of the Rhyme test procedure is presented in quiet from one loudspeaker in a distance of 4m in a reverberant environment (right part of Figure 4) and from an adjacent room with the door left ajar.

5) Subject assessment of speech in quiet in different room configurations (SE benefit)

The speech material is presented either from one loudspeaker or the tester by reading out loud in a distance of 2m, 4m and 8m in a reverberant environment and from an adjacent room with the door left ajar.

6) OLSA (hearing aid benefit)

For the hearing aid benefit part: diffuse cafeteria babble noise from 11 loudspeakers at 65.0 dB (marked with “N”). Target speech material are OLSA sentences presented from the front. Subjects are seated in the middle of the loudspeaker circle and are instructed to look to the front.

7) Real Ear Measurement

The measurements of the output of the fitted hearing aids will be conducted with a probe tube at the subject's right and left ear drums. For input signal presented from a loudspeaker at 0° in 1 m distance the ISTS (Holube et al. 2010) is used at three different presentation levels: 50 dB SPL, 65 dB SPL and 80 dB SPL. The determined measure is REAR (Real Ear Aided Response). This is a standard measurement during hearing aid fitting. The standard measurement equipment (Aurical from GN Otometrics) is used.

9 Statistical design and analysis

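### Objective 5-b rests on live reading by a tester who is not described as masked and whose voice level is not controlled, so a reader difference between Speech Enhancer ON and OFF would be confounded with the device effect

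*Combined protocol and SAP*

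**What the plan says.** **Blinding.** Section 4 states: "It is a single blinded study because all test conditions are implemented in the same hearing aid". The participant is the only party said to be unable to tell the settings apart; the tester and the investigator are not mentioned as masked. The same section adds: "The tested features can be activated via the MyPhonak APP by the subjects/investigator".

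**Stimulus.** In Section 6 item 4, "a novel is either read by the tester aloud (with soft voice) or presented by a loudspeaker". The two modes are assigned as "read out loud by the tester (with visual cues) and presented via loudspeaker (no visual cues"). Section 8 item 5 repeats the distances of 2, 4 and 8 m. Neither section gives a target level in dB, a level check, a recording or a fixed text for the live reading.

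**Objective.** Objective 5-b in Section 2 compares Speech Enhancer activated with not activated "for distant speech in a quiet situation with access to visual cues", on subjective intelligibility and listening effort.

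**Data.** "The subjective assessment will be repeated 14 times for the secondary objective". Each assessment yields a "rating on a 100-point scale per condition and per dimension", the dimensions being loudness, listening effort and intelligibility.

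**Analysis.** Section 9.3.2 f) analyses each listening condition separately, in a linear mixed model with subject as random effect, a likelihood ratio test and a Bonferroni correction over attributes. The divisor is not given. There is no term for reader or voice level.

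**The concern.** In the visual-cue condition the tester's voice is the stimulus. All three rated dimensions respond to how loudly and clearly a person speaks. If the reader is aware of the setting, even a small unintended change in level or articulation between ON and OFF readings goes straight into the ON–OFF contrast. Blinding the participant does not help, because the participant would be rating a stimulus that really is different. Randomised order and full crossover balance order effects, but they do not remove a shift tied to the setting itself. More participants would not help either: a systematic shift only becomes easier to declare significant.

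Section 4 calls the design confirmatory, and Section 5 intends the Speech Enhancer results as evidence of superiority for marketing use. A 5-b result in either direction would be open to an objection that none of the planned data could answer.

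**Working it through.** **1. The plan's own count.** Assessments per participant = 2 settings × (3 distances read live + 3 distances by loudspeaker + 1 adjacent room by loudspeaker) = 2 × 7 = 14, as stated. Live readings = 2 × 3 = 6 of 14, and these are all of the data for 5-b. With three dimensions each, that is 6 × 3 = 18 of 14 × 3 = 42 individual ratings.

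**2. Level control elsewhere in the plan.**

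| Test | Control of the presented sound |
|---|---|
| OLSA (Section 6 item 1) | noise fixed at 65 dB, speech level set by the adaptive procedure |
| WaKo (Section 6 item 3) | individually measured level, then reduced by 1 dB |
| Subjective assessment 5-a, 5-c (Section 6 item 4) | loudspeaker |
| Subjective assessment 5-b (Section 6 item 4) | tester's soft voice, no level given |

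Of these, only 5-b leaves the stimulus to a person who could vary it with the setting.

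**3. Illustration of what a reader shift could do.**

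Inputs from the plan: 22 participants (Section 9.1 e) and two-sided alpha 0.05 (Section 9.3.2).

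Assumptions, none of them in the plan:
- The true Speech Enhancer effect is zero.
- The reader shift is constant, with size d in SDs of the participant-mean ON–OFF difference.
- A paired t-test stands in for the planned mixed model.
- The Bonferroni divisor is 1, 2 (the attributes named in 5-b) or 3 (the questionnaire dimensions).

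Formula: P(significant) = P(|T| > c), where T is non-central t with 21 degrees of freedom and non-centrality d × √22, and c is the two-sided critical value. Here c = 2.080 at 0.05, 2.414 at 0.05/2 and 2.601 at 0.05/3.

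| d | d × √22 | at 0.05 | at 0.05/2 | at 0.05/3 |
|---|---|---|---|---|
| 0 (nominal) | 0 | 5.0% | 2.5% | 1.7% |
| 0.1 | 0.469 | 7.3% | 4.0% | 2.8% |
| 0.2 | 0.938 | 14.6% | 8.8% | 6.5% |
| 0.3 | 1.407 | 26.9% | 18.0% | 14.0% |
| 0.5 | 2.345 | 60.9% | 48.5% | 41.8% |

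With 20 participants the 0.05 column for d = 0.1 to 0.5 reads 7.1%, 13.6%, 24.7% and 56.5%.

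In scale points, a 3-point shift on the 100-point scale is d = 0.3, 0.2 or 0.15 if the SD of the paired difference is 10, 15 or 20 points. Those SDs are assumed as well.

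The table counts significant results for a shift of either sign. A shift that favours ON would create or inflate a benefit; one that favours OFF would hide or reverse it.

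**The case against.** **The tester may not know the setting.** A reader might infer that the tester knows whether Speech Enhancer is on. The documents do not say so. They do not state that tester and investigator are the same person, or who switches the program before a live reading. What stands is narrower: masking is described for the participant only, and the app sentence leaves the switching with the subjects or the investigator.

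**A false benefit is not the only possible outcome.** It is tempting to read the problem as one that favours the device. Nothing in the documents supports a direction, and a reader could equally speak up with the feature off. The instruction to use a soft voice asks for a constant manner, but it is not quantified.

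**The percentages are not evidence about this trial.** That is correct. The plan gives no SD, expected effect or voice-level variation for the questionnaire, and at 0.1 SD the inflation is slight. The table shows how the error rate depends on a shift that cannot be ruled out, not how large that shift will be.

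**The loudspeaker condition gives a comparison.** Objective 5-a uses the same participants, distances, settings and scales, so a 5-b effect with no counterpart in 5-a would be noticeable. It is at most an informal cross-check: visual cues differ as well, and Section 9.3.2 f) plans no comparison between listening conditions.

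**Live reading is deliberate.** Real speech with visual cues is a reasonable thing to test, and single blinding is disclosed. This argues for controlling the reading, not for dropping it.

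**Conclusion.** The point holds as a cheap improvement to one secondary objective. As written, a reader-related difference between ON and OFF readings cannot be separated from a Speech Enhancer effect in 5-b, and neither randomised order nor participant blinding prevents it. The conclusion rests on what the plan omits: no masking of the tester, no level control for the live voice and no level term in the model.

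The likely size of the bias cannot be derived from the documents. Under the assumed shifts, the rate of significant results runs from slightly above nominal to about 61% at 0.05, or about 42% at 0.05/3.

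A reader might extend the concern to the whole Speech Enhancer part. The documents do not support that: the other Speech Enhancer objectives use loudspeaker or test-procedure speech, and the primary endpoint is untouched. One wording does need clearing up. Section 8 item 5 can be read as allowing live reading from the adjacent room, whereas Section 6 item 4 assigns that condition (5-c) to the loudspeaker.

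**What to change.** - **Sections 6 item 4 and 8 item 5:** have the tester read to a fixed target level on a sound level meter, and log the level of every reading. State that the adjacent-room condition is by loudspeaker only, if that is the intention.
- **Section 4:** say who switches the program and whether the reader is masked. Where the fitting software or app allows, store ON and OFF as coded programs A and B, with a randomised mapping that is not shown to the reader. The documents do not show whether the device set-up permits this.
- **Section 9.3.2 f):** pre-specify that the ON and OFF reading levels are always reported, and that a level-adjusted sensitivity analysis of 5-b is always run. Making it conditional on an observed level difference would need a threshold and would let the data choose the analysis. State the Bonferroni divisor at the same time.
- **If the reader cannot be masked:** state this as a limit on the 5-b conclusion. Level adjustment does not correct for clearer speech or more visible articulation, so masking is the main protection and the logged level a partial one.

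The cost is a little set-up work and one logged level per reading, that is, 6 per participant. No extra visit or new outcome is needed. Whether masking needs a second person depends on the set-up.
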